### 10.3.1 Estimation of the number of HIV-1 infection endpoints at an interim analysis

The method for estimating the probability distribution of the number of HIV-1 infection endpoints by the end of Stage 1 is based on the following approach to simulating this trial. The trial is modeled as a combination of three processes—enrollment, dropout, and HIV-1 infection—and a large number of trials is simulated. The three processes are assumed independent and their distributions are taken to be Poisson, exponential, and exponential, respectively. Data are generated at the level of the individual participant, such that, for each participant, we obtain an enrollment time, an (underlying true) infection time, and a dropout time. Only the minimum of the infection and dropout times is observable, and the average value for this minimum is beyond the duration of the trial, such that neither event will be observed for most participants.

In the absence of observed trial data, the treatment arm-pooled as well as the treatment arm-specific parameters for the infection and dropout processes are chosen to match our pre-trial assumptions about these rates. In addition, the infection rate considers both the design alternative of  $VE = 50\%$  and the null hypothesis of  $VE = 0\%$  in the calculation of the total and treatment arm-specific numbers of endpoints. More specifically, treatment arm-pooled calculations in (a)–(c) and (e)–(g) assume

- pooled infection rate [MITT  $VE(0-7) = 25\%$  and  $VE(7-24) = 50\%$  scenario]:  $0.5 \times 0.042 + 0.5 \times \left(\frac{7}{24} \times 0.75 + \frac{17}{24} \times 0.5\right) \times 0.042 = 0.0330$  infections/person-year at-risk, and
- pooled infection rate [ $VE(0-24) = 0\%$  scenario]: 0.042 infections/person-year at-risk.

Conditioning on interim data, a complete time-to-event data set is simulated for the MITT cohort, and the PP cohort is extracted at the end.

We also assume a treatment arm-pooled dropout rate of 0.10 dropouts/person-year at-risk.

Treatment arm-specific calculations in (d) and (h) assume

- infection rate in the control arm: 0.042 infections/person-year at-risk,
- infection rate in the vaccine arm [MITT  $VE(0-7) = 25\%$  and  $VE(7-24) = 50\%$  scenario]:  $(\frac{7}{24} \times 0.75 + \frac{17}{24} \times 0.5) \times 0.042 = 0.0241$  infections/person-year at-risk, and
- infection rate in the vaccine arm [PP  $VE(7-24) = 50\%$  scenario]:  $0.5 \times 0.042 = 0.021$  infections/person-year at-risk.

In each treatment arm, the dropout rate is assumed to be 0.10 dropouts/person-year at-risk.

The first step in simulating each trial is to enroll a certain number of participants per week according to a random draw from a Poisson distribution with rate parameter as listed above. Enrollment continues week-by-week until a total of 2,600 participants is reached. Second, each participant is assigned an exact enrollment day, uniformly distributed within their enrollment week. Following enrollment, the infection and dropout times are drawn from their respective exponential distributions, and the lesser of the two is recorded as occurring at the given time (possibly outside the time-window of the trial). We consider dropout events to have occurred at the dropout time (in days) that was generated (assuming it was less than the infection time). For participants who become HIV-1 infected, we record their time of diagnosis as the time of the first study visit following the true infection time. It is this time of diagnosis that we observe for infected participants.

A modification of the above procedure for simulating an efficacy trial is used for estimating metrics of futility to assess VE at a given interim analysis. The modification entails using the observed trial data to estimate parameters of the processes, rather than relying entirely on pre-trial assumptions. In particular:

- enrollment rate: if enrollment is incomplete, estimated based on the rate observed in approximately the last 6 months in the study,
- infection rate: drawn from a posterior distribution of the infection rate formed by combining the observed data with our prior specification about the infection rate based on the pre-trial assumptions, and
- dropout rate: estimated based on the treatment arm-pooled rate observed to date.

The rationale for a Bayesian approach for the infection rate (see Section 10.3.2 for details) is to help stabilize the infection rate early in the trial when insufficient time will have passed to accrue many infections. If we were to rely solely on the observed infections, we might by chance obtain very low rates, which would lead to an unrealistic prediction of the number of endpoints.

We consider various different gamma prior distributions for the infection rate in each of scenarios (i)–(iii) reflecting different weights assigned to the prior distribution (see Section 10.3.2 for details). Gamma distributions are considered because they are conjugate to the exponential distribution used for generating future infection data.

At a given interim analysis,  $10^4$  trials are simulated using the above procedure and treatment arm-pooled infection and dropout rates for estimates in (a)–(c) and (e)–(g). Separately, another set of  $10^4$  trials is simulated using the above procedure, treatment arm-specific infection rates, and the treatment arm-pooled dropout rate for estimates in (d) and (h). Each of these trials yields a projected number of infections by the end of Stage 1. These projected numbers of infections from each trial will be used to estimate the entire distribution of the number of infections by the end of Stage 1. The probability of reaching the target number of infections will be estimated as the proportion of trials with the projected number of infections greater than or equal to the target.

Figures on enrollment, HIV-1 incidence and dropout over time will also be included to aid interpretation of the results.

### 10.3.2 A Bayesian model for the HIV-1 incidence rate in estimation of the number of HIV-1 infection endpoints at an interim analysis

Let  $n_k$  and  $T_k$  denote, respectively, the infection count and the observed total person-time at risk at the time of the  $k$ -th futility analysis, pooling over all treatment arms. Additionally, let  $T^*$  denote the estimated total person-time at risk for the primary efficacy analysis at the end of Stage 1. Let the prior distribution of the pooled HIV-1 incidence rate  $p$  be  $\text{Ga}(\alpha, \beta)$  parametrized such that the prior mean  $E p = \alpha/\beta$  (the same Bayesian method applies to the treatment arm-specific HIV-1 incidence rate). In scenario (i) for the treatment arm-pooled incidence rate, we additionally consider a robust prior distribution described in Section 10.3.2.1 used in the calculation evaluating the enrollment modifications guideline.

Generally, assuming that, conditional on  $p$ , the times to infection follow  $\text{Exp}(p)$ , the posterior mean of  $p$  at the time of the  $k$ -th analysis equals

$$\begin{aligned} E[p \mid \text{data}] &= \frac{\alpha + n_k}{\beta + T_k} \\ &= \frac{\alpha}{\beta} \frac{\beta}{\beta + T_k} + \frac{n_k}{T_k} \frac{T_k}{\beta + T_k}, \end{aligned} \quad (3)$$

i.e., the posterior mean can be interpreted as a convex combination of the prior mean and the observed incidence rate. For a given  $\beta > 0$ , the weight on the prior mean at the first analysis depends on the accumulated person-time at risk ( $T_1$ ), and the weight will decrease in subsequent analyses because  $\beta/(\beta + T_k)$  is a decreasing function of  $T_k$ , which is a desirable Bayesian property.

In order to identify  $\alpha$  and  $\beta$ , it is desirable that the prior mean equals the pre-trial assumed treatment arm-pooled incidence rate  $p^*$  (e.g., under PP VE(7–24)=50%,  $p^* = 0.5 \times 0.042 + 0.5 \times 0.5 \times 0.042 = 0.0315$ ), i.e.,

$$\frac{\alpha}{\beta} = p^*. \quad (4)$$

Furthermore, we propose to consider three values of  $\beta$  that correspond to the weights  $w = \frac{1}{2}$ ,  $\frac{1}{3}$  and  $\frac{1}{4}$  on the prior mean at the time when 50% of the estimated total person-time at risk has been accumulated, i.e., for each value of  $w$ ,  $\beta$  is defined as the solution to the equation

$$\frac{\beta}{\beta + T^*/2} = w.$$

It follows that

$$\beta = \beta(w, T^*) = \frac{wT^*}{2(1-w)}, \quad (5)$$

and the estimation of  $T^*$  is described in Section 10.3.2.2. For  $w = \frac{1}{2}$ ,  $\frac{1}{3}$  and  $\frac{1}{4}$ , we obtain  $\beta = \frac{T^*}{2}$ ,  $\frac{T^*}{4}$ , and  $\frac{T^*}{6}$ , respectively.

At the  $k$ -th futility analysis and for each of the three values of  $\beta$ , we will sample the treatment arm-pooled HIV-1 incidence rate from the posterior  $\text{Ga}(\alpha + n_k, \beta + T_k)$  for generating future data and report the weight  $\frac{\beta}{\beta + T_k}$  on the prior mean in the convex combination (3).

### 10.3.2.1 A robust prior model for the HIV-1 incidence rate in the calculation evaluating the guideline for enrollment modifications

The robust prior model (Schmidli et al., 2014) is implemented for the guideline to trigger enrollment modifications since it is designed to maximize the probability of meeting the guideline for large downward deviations from the protocol-assumed incidence rates, while minimizing a false trigger for protocol-assumed incidence rates.

The prior distribution of  $p$  is defined as a weighted mixture of two gamma distributions,

$$(1 - w_R)\text{Ga}(\alpha_I, \beta_I) + w_R\text{Ga}(\alpha_V, \beta_V),$$

where we set  $w_R = 0.2$ , and  $\text{Ga}(\alpha_V, \beta_V)$  and  $\text{Ga}(\alpha_I, \beta_I)$  represent the weakly informative and informative component of the mixture prior, respectively. The parameters  $\beta_V$  and  $\beta_I$  are calculated following (5) with  $w = 1/1000$  and  $w = 1/3$ , respectively (and  $T^*$  per Section 10.3.2.2). Subsequently,  $\alpha_V$  and  $\alpha_I$  are calculated following (4) with  $p^*$  set to the pre-trial assumed treatment arm-pooled MITT incidence rate of 0.0330 infections/person-year at risk for both components of the mixture (i.e., assuming  $\text{VE}(0-7) = 25\%$ ,  $\text{VE}(7-24) = 50\%$ , and a constant placebo incidence rate over time).

The posterior distribution at the time of the  $k$ -th analysis is derived following the conjugacy principle, as in (3), which results in a mixture of conjugate posteriors with updated weights

$$(1 - \tilde{w}_{R,k})\text{Ga}(\alpha_I + n_k, \beta_I + T_k) + \tilde{w}_{R,k}\text{Ga}(\alpha_V + n_k, \beta_V + T_k),$$

where

$$\tilde{w}_{R,k} \propto w_{R,k}f_V / \{w_{R,k}f_V + (1 - w_{R,k})f_I\}$$

with  $f$  equal to

$$f = \frac{\Gamma(\alpha + n_k)/(\beta + T_k)^{\alpha+n_k}}{\Gamma(\alpha)/\beta^\alpha}$$

(see, e.g., Bernardo and Smith, 2000, Section 5.2.3, pages 279–282).

### 10.3.2.2 Estimation of the total person-years at risk by the end of Stage 1

The total target sample size is  $N = 2600$ , the duration of Stage 1 follow-up per participant is  $\tau = 2$  years, the pre-trial assumed dropout rate is  $d^* = 0.1$  dropouts per person-year at risk (PYR), and, in the MITT  $VE(0-7) = 25\%$  and  $VE(7-24) = 50\%$  scenario, the pre-trial assumed treatment arm-pooled HIV-1 incidence rate is  $p^* = 0.5 \times 0.042 + 0.5 \times \left(\frac{7}{24} \times 0.75 + \frac{17}{24} \times 0.5\right) \times 0.042 = 0.0330$  cases per PYR.

We consider the standard right-censored failure time analysis framework. Denoting the failure and censoring times as  $T$  and  $C$ , respectively, we assume that  $T$  is independent of  $C$ ,  $T \sim \text{Exp}(p^*)$ , and  $C \sim \text{Exp}(d^*)$ . It follows that  $X := \min(T, C) \sim \text{Exp}(p^* + d^*)$  and

$$\begin{aligned} T^* &= N \times E[\min(X, \tau)] \\ &= N \times \{E[X | X \leq \tau] P(X \leq \tau) + \tau P(X > \tau)\} \\ &= N \times \left\{ (p^* + d^*) \int_0^\tau x \exp^{-(p^*+d^*)x} dx + \tau \exp^{-(p^*+d^*)\tau} \right\} \\ &= N \times \frac{1 - \exp^{-(p^*+d^*)\tau}}{p^* + d^*}. \end{aligned}$$

This results in  $T^* = 4565.85$  PYRs. For comparison, if all  $N$  participants were followed for  $\tau$  years, the total PYRs would be  $N\tau = 5200$  years.

Subsequently, for  $T^* = 4565.85$  PYRs, if  $T_1 = 0.2T^*$ , the weights  $\frac{\beta}{\beta+T_1}$  on the prior mean at the first futility analysis in the MITT cohort corresponding to  $w = \frac{1}{2}$ ,  $\frac{1}{3}$ , and  $\frac{1}{4}$  are 0.71, 0.56, 0.45, respectively. If  $T_1 = 0.3T^*$ , the respective weights on the prior mean are 0.63, 0.45, and 0.36.

## 10.4 Monitoring for Performance Standards of Quality of Trial Conduct

The protocol team and study investigators will have performance standards regarding the quality of trial conduct in addition to the study endpoint rate. Some of these use standard metrics detailed in the Network Evaluation Metrics and Standards document, whereas others are specific to the HVTN 705 trial. Some of these standards will relate to achievement of targeted levels of:

1. participant enrollment into the trial (targets based on protocol assumptions).
2. retention of participants (target 5% annual dropout or less, with minimally acceptable level of no more than 10% annual dropout; also target 90% visit attendance among participants under follow-up [NEC standard]).

3. adherence to study interventions (target 95% adherence for receipt of first three doses, with minimally acceptable level of 80%; and target 90% adherence for receipt of first four doses, with minimally acceptable level of 80%).
4. quality and timeliness of HIV-1 diagnostic testing.
5. quality and timeliness of data collected on case report forms.

#### 10.4.1 Expanded details for reporting on item 4: quality and timeliness of HIV-1 diagnostic testing

1. **Timeliness:** Turnaround time from blood collection to diagnostic reporting is summarized. This process monitors the site, the site-processing lab, the shipping company and the actual diagnostics lab. In addition the turnaround time from arrival in the lab to reporting is monitored, which isolates the turnaround time to the lab.
2. **Quality:** No additional monitoring for HIV-1 diagnostic quality is done beyond the fact that the labs participate in CAP and VQA and they are all audited annually by DAIDS.

#### 10.4.2 Expanded details for reporting on item 5: quality and timeliness of data collected on case report forms

This reporting will use NEC standard metrics, as detailed in the Network Evaluation Metrics and Standards document (pages 12-14). In summary, the reporting outputs are as follows:

1. **For Quality:** For **QC Rate**, the standard metric for satisfactory quality is < 10 QCs per 100 pages. The denominator for this metric includes the total number of pages entered in the database during the time period. For refaxes, only the most recent page faxed is included. All CRF pages faxed to SCHARP are included in this calculation. Total CRF pages are labeled (Total Pages1) in the DMQ table.  
For **QC Resolution**, the standard metric is > 80% of QCs resolved in < 7 calendar days.  
For **Percent EDCd**, note that quality tends to be higher when pages are submitted via EDC (real time validation, faster submissions, etc), and this metric incentivizes sites to use EDC.
2. **Timeliness:** The standard metric for CRF Submission Rate (% pages faxed/EDCd on time) is > 90% of pages submitted within < 4 calendar days. The denominator for this metric is not total pages, as it excludes pages that, according to study operations, may not be completed and/or faxed immediately following a study visit (e.g., screening visit forms). Log-based forms are also not included. For refaxes, only the initial page faxed

is included. Only time-critical CRF forms are calculated. Screening and log based forms are excluded. CRFs included in this calculation are labeled (Total Pages2). HIV test results are excluded.

The DSMB and the leadership of the HVTN 705 trial will monitor whether the trials are achieving at least minimally acceptable levels of key performance standards. The DSMB will make recommendations to improve areas that are deficient. Termination of a trial would be considered if it appears unlikely that minimally acceptable performance will be achieved.

## 11 Statistical Software

All analyses described in this SAP will be conducted in validated instances of *R* and *SAS*.

## 12 Roles of Study Statisticians

HVTN SDMC statisticians will be blinded or unblinded to treatment group. During protocol development and after primary follow-up is completed, there will be no distinction between the roles; both types of statisticians will be responsible for designing and analyzing the study. During the primary follow-up period, however, only the treatment-unblinded statistician(s) will see interim data broken down by treatment group. Their role will be to conduct the interim monitoring and to produce and present reports on accruing data to the study DSMB. During the primary follow-up period, treatment-blinded statisticians will see only the interim data pooled across study groups. This way, treatment-blinded statisticians can assist protocol leadership in making decisions about modifications to the protocol without being influenced by interim efficacy results.

## Appendix A Mock Tables and Figures for DSMB Closed Report

Mock tables and figures for the DSMB Closed Report are included below. The Closed Report summarizes trial information pooled across the treatment groups (labeled Total) and by masked treatment assignment (labeled A and B). A subset of these tables and figures will form the Open Report, in which trial information is reported pooled across the treatment groups.

Off Study Early	xxxx (xx.x%)	xxxx (xx.x%)	xxxx (xx.x%)

\*Enrollment implies receipt of the first vaccination.

+This category reports participants randomized prior to the cutoff date, but not vaccinated prior to it.

Study completion requires at least 24 months of follow-up for uninfected participants and 6 months post-diagnosis for infected participants.

**Table BL1. Baseline Participant Characteristics, by Treatment Assignment  
Population: Full Analysis Set (N = xxxx)**

	Total	A	B
Total Enrolled	xxx	xxx	xxx
Age (Years)			
18 – 20	xxx (xx.x%)	xxx (xx.x%)	xxx (xx.x%)
21 – 30	xxx (xx.x%)	xxx (xx.x%)	xxx (xx.x%)
31 – 35	xxx (xx.x%)	xxx (xx.x%)	xxx (xx.x%)
Median (Min, Max)	xx (xx, xx)	xx (xx, xx)	xx (xx, xx)
BMI			
<18.5	xxx (xx.x%)	xxx (xx.x%)	xxx (xx.x%)
18.5-25	xxx (xx.x%)	xxx (xx.x%)	xxx (xx.x%)
≥25	xxx (xx.x%)	xxx (xx.x%)	xxx (xx.x%)
Race +			
Black	xxx (xx.x%)	xxx (xx.x%)	xxx (xx.x%)
Colored/Mixed	xxx (xx.x%)	xxx (xx.x%)	xxx (xx.x%)
White	xxx (xx.x%)	xxx (xx.x%)	xxx (xx.x%)
Indian	xxx (xx.x%)	xxx (xx.x%)	xxx (xx.x%)
Asian	xxx (xx.x%)	xxx (xx.x%)	xxx (xx.x%)
Other	xxx (xx.x%)	xxx (xx.x%)	xxx (xx.x%)
Multiple	xxx (xx.x%)	xxx (xx.x%)	xxx (xx.x%)

+Participants may report more than one racial category – those who do so are categorized as ‘Multiple’.  
Some counts may not total to the number of participants, due to non-response. Missingness is not included explicitly as it is minimal.

**Table BL2. Baseline Risk Behaviors, by Treatment Assignment**

**Population: Full Analysis Set (N = xxxx)**

**The reference time-period for these questions is the previous month, except for Condom Use**

	Total	A	B
Total Enrolled	xxx (xx.x%)	xxx (xx.x%)	xxx (xx.x%)
Number of Sex Partners in the Last Month			
0	xxx (xx.x%)	xxx (xx.x%)	xxx (xx.x%)
1	xxx (xx.x%)	xxx (xx.x%)	xxx (xx.x%)
2	xxx (xx.x%)	xxx (xx.x%)	xxx (xx.x%)
3-4	xxx (xx.x%)	xxx (xx.x%)	xxx (xx.x%)
>=5	xxx (xx.x%)	xxx (xx.x%)	xxx (xx.x%)
Median (Min, Max)	xx (xx, xx)	xx (xx, xx)	xx (xx, xx)
Condom use, general frequency			
Always	xxx (xx.x%)	xxx (xx.x%)	xxx (xx.x%)
Sometimes	xxx (xx.x%)	xxx (xx.x%)	xxx (xx.x%)
Never	xxx (xx.x%)	xxx (xx.x%)	xxx (xx.x%)
Anal Sex			
Yes	xxx (xx.x%)	xxx (xx.x%)	xxx (xx.x%)
Had an HIV+ Partner			
Yes	xxx (xx.x%)	xxx (xx.x%)	xxx (xx.x%)
Unprotected Sex with HIV+ Partner			
Yes	xxx (xx.x%)	xxx (xx.x%)	xxx (xx.x%)
Exchange of Sex for Money/Gifts			
Yes	xxx (xx.x%)	xxx (xx.x%)	xxx (xx.x%)
Diagnosed with or treated for STI			
Yes	xxx (xx.x%)	xxx (xx.x%)	xxx (xx.x%)
Alcohol Use and Unprotected Sex			
Never	xxx (xx.x%)	xxx (xx.x%)	xxx (xx.x%)
1-2 times	xxx (xx.x%)	xxx (xx.x%)	xxx (xx.x%)
3-5 times	xxx (xx.x%)	xxx (xx.x%)	xxx (xx.x%)
6 or more times	xxx (xx.x%)	xxx (xx.x%)	xxx (xx.x%)

Participants are not required to answer these questions, so counts may not match the number of participants. Missingness is not included explicitly as it is minimal. Percentages are relative to the total number of participants enrolled.

**Table STATUS1. Study Status and Reasons for Early Study Termination, by Treatment Assignment Population: Full Analysis Set (N = xxxx)**

	Total		A		B	
Total Enrolled	xxx	(xx.x%)	xxx	(xx.x%)	xxx	(xx.x%)
Status						
On Study, In Trt Phase	xxx	(xx.x%)	xxx	(xx.x%)	xxx	(xx.x%)
On Study, Completed Trt Phase	xxx	(xx.x%)	xxx	(xx.x%)	xxx	(xx.x%)
On Study, Discontinued Trt	xxx	(xx.x%)	xxx	(xx.x%)	xxx	(xx.x%)
Completed Study, Completed Trt Phas	xxx	(xx.x%)	xxx	(xx.x%)	xxx	(xx.x%)
Completed Study, Discontinued Trt	xxx	(xx.x%)	xxx	(xx.x%)	xxx	(xx.x%)
Off Study Early, Completed Trt Phase	xxx	(xx.x%)	xxx	(xx.x%)	xxx	(xx.x%)
Off Study Early, Discontinued Trt	xxx	(xx.x%)	xxx	(xx.x%)	xxx	(xx.x%)
Reasons for Early Study Termination						
Death	xxx	(xx.x%)	xxx	(xx.x%)	xxx	(xx.x%)
Participant refused further participation	xxx	(xx.x%)	xxx	(xx.x%)	xxx	(xx.x%)
Unable to adhere to visit schedule	xxx	(xx.x%)	xxx	(xx.x%)	xxx	(xx.x%)
Participant relocated	xxx	(xx.x%)	xxx	(xx.x%)	xxx	(xx.x%)
Unable to contact	xxx	(xx.x%)	xxx	(xx.x%)	xxx	(xx.x%)
Investigator decision	xxx	(xx.x%)	xxx	(xx.x%)	xxx	(xx.x%)
Inappropriate enrollment	xxx	(xx.x%)	xxx	(xx.x%)	xxx	(xx.x%)
Duplicate screening/enrollment	xxx	(xx.x%)	xxx	(xx.x%)	xxx	(xx.x%)
Early study closure	xxx	(xx.x%)	xxx	(xx.x%)	xxx	(xx.x%)
Participant incarcerated	xxx	(xx.x%)	xxx	(xx.x%)	xxx	(xx.x%)
Other	xxx	(xx.x%)	xxx	(xx.x%)	xxx	(xx.x%)
Early Study Termination Due to an AE	xxx	(xx.x%)	xxx	(xx.x%)	xxx	(xx.x%)

**Table STATUS2. Vaccination Status and Reasons for Discontinuation, by Treatment Assignment**

**Population: Full Analysis Set (N = xxxx)**

	Total	A	B
Total Enrolled	xxx	xxx	xxx
Treatment Status			
In Trt Phase	xxx (xx.x%)	xxx (xx.x%)	xxx (xx.x%)
Completed Trt Phase	xxx (xx.x%)	xxx (xx.x%)	xxx (xx.x%)
Discontinued Trt	xxx (xx.x%)	xxx (xx.x%)	xxx (xx.x%)
Reasons for Discontinuation of Vacc.			
Death	xxx (xx.x%)	xxx (xx.x%)	xxx (xx.x%)
Adverse Experience	xxx (xx.x%)	xxx (xx.x%)	xxx (xx.x%)
Reactogenicity Symptom	xxx (xx.x%)	xxx (xx.x%)	xxx (xx.x%)
Other Clinical Event	xxx (xx.x%)	xxx (xx.x%)	xxx (xx.x%)
Unable to Contact / Out of Window	xxx (xx.x%)	xxx (xx.x%)	xxx (xx.x%)
Participant Refused Vaccination	xxx (xx.x%)	xxx (xx.x%)	xxx (xx.x%)
Other	xxx (xx.x%)	xxx (xx.x%)	xxx (xx.x%)
Missing	xxx (xx.x%)	xxx (xx.x%)	xxx (xx.x%)

**Table RETEN1. Visit Retention, by Treatment Assignment**  
**Population: Full Analysis Set (N = xxxx)**

	Total	A	B
Total Enrolled	xxx	xxx	xxx
Month 3 / Vaccination 2			
Expected* for visit or terminated +	xxx	xxx	xxx
Completed	xxx (xx.x%)	xxx (xx.x%)	xxx (xx.x%)
Missed	xxx (xx.x%)	xxx (xx.x%)	xxx (xx.x%)
Terminated +	xxx (xx.x%)	xxx (xx.x%)	xxx (xx.x%)
Month 6 / Vaccination 3			
Expected* for visit or terminated +	xxx	xxx	xxx
Completed	xxx (xx.x%)	xxx (xx.x%)	xxx (xx.x%)
Missed	xxx (xx.x%)	xxx (xx.x%)	xxx (xx.x%)
Terminated +	xxx (xx.x%)	xxx (xx.x%)	xxx (xx.x%)
Month 6.5 / Post-Vaccination			
Expected* for visit or terminated +	xxx	xxx	xxx
Completed	xxx (xx.x%)	xxx (xx.x%)	xxx (xx.x%)
Missed	xxx (xx.x%)	xxx (xx.x%)	xxx (xx.x%)
Terminated +	xxx (xx.x%)	xxx (xx.x%)	xxx (xx.x%)
Month 12 / Vaccination 4			
Expected* for visit or terminated +	xxx	xxx	xxx
Completed	xxx (xx.x%)	xxx (xx.x%)	xxx (xx.x%)
Missed	xxx (xx.x%)	xxx (xx.x%)	xxx (xx.x%)
Terminated +	xxx (xx.x%)	xxx (xx.x%)	xxx (xx.x%)

\*Participants are considered expected for a visit when they reach the end of their visit window.

+Terminated prior to completion of visit as defined by submission of a specimen collection form.

Participants that terminate from the study continue to be marked as terminated and counted at subsequent visits.

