**Table TRTADH2. Overall Cumulative Treatment Adherence**

**Population: Full Analysis Set (N = xxxx)**

	Total	A	B
Month 3 / Vaccination 2			
Expected or terminated	xxx	xxx	xxx
Received all treatments	xxx (xx.x%)	xxx (xx.x%)	xxx (xx.x%)
Missed 1 treatment, on-trt	xxx (xx.x%)	xxx (xx.x%)	xxx (xx.x%)
Discontinued treatment*, on-study	xxx (xx.x%)	xxx (xx.x%)	xxx (xx.x%)
Terminated prior to vaccination	xxx (xx.x%)	xxx (xx.x%)	xxx (xx.x%)
Month 6 / Vaccination 3			
Expected or terminated	xxx	xxx	xxx
Received all treatments	xxx (xx.x%)	xxx (xx.x%)	xxx (xx.x%)
Missed 1 treatment, on-trt	xxx (xx.x%)	xxx (xx.x%)	xxx (xx.x%)
Missed 2 treatments, on-trt	xxx (xx.x%)	xxx (xx.x%)	xxx (xx.x%)
Discontinued treatment*, on-study	xxx (xx.x%)	xxx (xx.x%)	xxx (xx.x%)
Terminated prior to vaccination	xxx (xx.x%)	xxx (xx.x%)	xxx (xx.x%)
Month 12 / Vaccination 4			
Expected or terminated	xxx	xxx	xxx
Received all treatments	xxx (xx.x%)	xxx (xx.x%)	xxx (xx.x%)
Missed 1 treatment, on-trt	xxx (xx.x%)	xxx (xx.x%)	xxx (xx.x%)
Missed 2 or more treatments, on-trt	xxx (xx.x%)	xxx (xx.x%)	xxx (xx.x%)
Discontinued treatment*, on-study	xxx (xx.x%)	xxx (xx.x%)	xxx (xx.x%)
Terminated prior to vaccination	xxx (xx.x%)	xxx (xx.x%)	xxx (xx.x%)

\*Discontinued treatment at or before the indicated visit..

HVTN 705/VAC89220HPX2008

Closed Report for DSMB meeting on [Date]. Data cutoff date: [Date].

Table PREG1. Pregnancy Listing  
Population: Full Analysis Set (N = xxxx)

Trt	Publication ID	Pregnancy Outcome	LMP Onset Date	Pregnancy Outcome date	Date of Last Vacc. Prior to Outcome	Time from Prior Vacc. To LMP	# Vacc. Prior to LMP	# Vacc. Prior to Outcome	Total # Vacc.
A	XXX-XXXX	text	ddMMMyyyy	ddMMMyyyy	ddMMMyyyy	text	text	X	XX
A	XXX-XXXX	text	ddMMMyyyy	ddMMMyyyy	ddMMMyyyy	text	text	X	XX
A	XXX-XXXX	text	ddMMMyyyy	ddMMMyyyy	ddMMMyyyy	text	text	X	XX
	.								
B	XXX-XXXX	text	ddMMMyyyy	ddMMMyyyy	ddMMMyyyy	text	text	X	XX
B	XXX-XXXX	text	ddMMMyyyy	ddMMMyyyy	ddMMMyyyy	text	text	X	XX
B	XXX-XXXX	text	ddMMMyyyy	ddMMMyyyy	ddMMMyyyy	text	text	X	XX

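### The DSMB retention and adherence tables put no visit-window condition on terminated women, so until the last enrollee's window closes the Month 12 row overstates loss and understates dose receipt

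*SAP*

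**What the plan says.** SAP Appendix A holds the mock tables for the DSMB Closed Report. In RETEN1 each visit's percentages rest on a row labelled "Expected* for visit or terminated". The footnotes define its two halves separately:

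- On-study women: "Participants are considered expected for a visit when they reach the end of their visit window".
- Women who have left: "Terminated prior to completion of visit as defined by submission of a specimen collection form", followed by "Participants that terminate from the study continue to be marked as terminated and counted at subsequent visits".

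TRTADH1 carries the same footnotes. TRTADH2, the cumulative all-doses table, uses the label "Expected or terminated" but defines neither term.

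SAP 10.4 sets performance standards. For adherence it gives, among others, "target 90% adherence for receipt of first four doses, with minimally acceptable level of 80" percent. For retention it gives "target 5% annual dropout or less, with minimally acceptable level of no more than 10% annual dropout", plus a visit-attendance target among participants under follow-up. SAP 10.4.2 closes with "Termination of a trial would be considered if it appears unlikely that minimally acceptable performance will be achieved". Section 10.4 does not define the denominator of the four-dose standard and does not name a source table.

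**The concern.** The two halves of the denominator have different entry rules. An on-study woman joins the Month 12 row only at the close of her own Month 12 window. A woman who left at Month 2 meets the terminated definition for every later visit, and nothing printed makes her wait until her window would have closed. Losses are then drawn from everyone enrolled so far, and non-losses only from early enrollees. While recent enrollees remain undue, a trial running exactly on its design shows inflated loss and depressed dose receipt, and then appears to recover by itself. DSMB reports are 6-monthly, so some fall within that period.

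**Working it through.** **Check of the dropout model.** The documents give no expected values for these tables. The same exponential dropout model underlies the SAP's person-years figure (section 10.3.2.2): 2600 × (1 − e^(−0.133×2)) / 0.133 = 4565.85, as stated there.

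**Inputs**

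- 2,600 women over 14 months, half rate in the first 3 (Protocol 6.4.1). The full rate is 2600 / (1.5 + 11) = 208 a month, with 104 a month at first.
- Dropout 0.10 per person-year (SAP 10.3.1).
- Upper visit window W: not given, held in the Study Specific Procedures (Protocol 9.10). Assumed 0, 1 or 2 months.
- HIV infection and on-study treatment discontinuation are not modelled.

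**True values.** Loss before Month 12 is 1 − e^(−0.10) = 9.5%; before Month 6, 1 − e^(−0.05) = 4.9%; before Month 3, 1 − e^(−0.025) = 2.5%.

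**Month 12 row as printed, report at month 18**

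- Terminated, enrolled by month 6: (312 + 3 × 208) × 0.0952 = 936 × 0.0952 = 89.1.
- Terminated, enrolled in months 6–14: each woman has 4 to 12 months since enrollment, giving 208 × [8 − 120 × (e^(−4/120) − e^(−12/120))] = 208 × 0.5146 = 107.0.
- Total terminated: 196.1.
- Expected: women enrolled by month 6 − W, times 0.9048. W = 0: 936 × 0.9048 = 846.9. W = 1: 728 × 0.9048 = 658.7. W = 2: 520 × 0.9048 = 470.5.
- Loss shown: 196.1/1043.0 = 18.8%; 196.1/854.8 = 22.9%; 196.1/666.6 = 29.4%.

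With W = 1, only 728 × 0.0952 = 69 of the 196 terminated women belong to enrollees whose window has closed.

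**Other report dates, same method**

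| Report month | Terminated | Loss shown, W = 0 | W = 1 | W = 2 |
|---|---|---|---|---|
| 14 | 131 | 41% | 58% | 100% (no window closed) |
| 16 | 167 | 26% | 37% | 47% |
| 18 | 196 | 19% | 23% | 29% |
| 20 | 219 | 15% | 17% | 21% |
| 24 | 244 | 11% | 12% | 13% |
| 28 | 247 | 9.5% | 9.5% | 9.5% |

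The last woman enrolls at month 14, so her Month 12 window closes at 14 + 12 + W, that is months 26 to 28.

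**Dose receipt in the Month 12 row.** If every on-study woman is dosed, receipt shown is 100% minus loss. At month 18 that is 81%, 77% and 71% for W = 0, 1 and 2; the true value is 90.5%. If 5% of on-study women miss the dose (an assumption), it is 77%, 73% and 67%, against 0.905 × 0.95 = 86%.

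**Other rows, report at month 12.** Month 6 loss shows 7.9–13.4% against 4.9%. Month 3 loss shows 3.0–4.0% against 2.5%.

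**Sensitivity.** At 5% annual dropout, Month 12 loss at month 16 shows about 15–30% against 4.9%. If accrual took about 19 months (an assumption), loss at month 18 shows 20–31% at 10% dropout.

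**The case against.** The footnote gives no timing. It can be read as an instruction not to drop leavers as later visits fall due; if programmers added each leaver only when her window would have closed, the bias would be zero. That is possible, but the text does not say it, and the same one-line definition settles the matter either way.

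Four further objections stand and limit the point.

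- **Retention standard.** A reader might infer that RETEN1 would show the 10% dropout limit breached. It cannot. That standard is an annual rate, and the attendance target excludes women who have left. The DSMB also sees dropout over time and early terminations against total enrolled.
- **Adherence standard.** A reader might infer a proven false breach of 80%. The documents do not establish one. Section 10.4 names no table; the standard concerns receipt of the first four doses, while TRTADH1 shows each dose separately; and TRTADH2 lacks the footnotes. The 86% benchmark also depends on who misses doses: with independent 5% misses at doses 2, 3 and 4, true four-dose receipt is 0.905 × 0.95³ = 78%, already below 80%. With no misses and no window, the Month 12 row at month 18 shows 81%.
- **Timing.** The 80% minimum entered in SAP version 3.4 (July 18, 2022). The last enrollee's Month 24 target was May 25, 2021, so her Month 12 visit fell around May 2020. No report issued under that version would still show the distortion.
- **Consequence.** Termination is something to be considered on a forward-looking judgement, not triggered by one row. The shells also print denominators and total enrolled, so an immature row is partly visible.

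**Conclusion.** The point holds as a defect in the table definitions. As printed, RETEN1 and TRTADH1, and TRTADH2 by its shared label, overstate loss and understate dose receipt at a visit until the last enrollee's window for that visit closes. The effect is large in the Month 12 row, moderate at Month 6, and small at Month 3 after the first reports. It is not confined to accrual: on the 14-month plan, the month-18 and month-24 reports both come after enrollment ends.

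The direction follows from the printed definitions for any window length. The sizes rest on planned accrual, 10% annual exponential dropout and the assumed 0–2 month window. Both arms are affected alike in expectation, so the arm comparison is not biased, and no efficacy analysis or efficacy stopping boundary uses these rows. What remains is a risk that a DSMB member sets an immature Month 12 percentage beside an adherence minimum. With accrual long finished, the practical value lies in reading past reports correctly and in not reusing the shells unchanged.

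**What to change.** In RETEN1, TRTADH1 and TRTADH2, define one denominator for each visit row: all enrolled women for whom the end of that visit's window, counted from their own enrollment date, is on or before the data cutoff, whether or not they have terminated. Count a terminated woman in the row only on that condition, and print the definition under all three tables. On the model above this gives 9.5% Month 12 loss at every report in which any woman is due.

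In SAP 10.4, state that the dose-receipt standards use the same denominator and name the table that supplies them. The cost is a footnote, a denominator definition and a small programming change, with no new data.
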